7.1. Discontinuation of Study Drug

Subjects who discontinue study drug will complete the Week 52/Early Withdrawal assessments specified in the Schedule of Assessments (Section 1.3).

Reasons for discontinuation from the study drug include the following:

- Any AE of urinary retention
- Any occurrence of PVR volume \geq 300 mL

Discontinuation of study drug for abnormal liver function should be considered by the investigator when a subject meets all of the conditions outlined in Section 8.4.6.2 for Hy's law or if the investigator believes that it is in best interest of the subject (reason for discontinuation will be AE).

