Unscheduled visits will be assigned to a study visit using the all-inclusive windows defined in Section 4.2.4. However, data summaries for non-diary data will only report visits that are planned assessment time points for each parameter, according to the Time and Events table. All

visits for bladder diary data will be fully derived as described in section 4.2.4.2. Assessments at unscheduled visits will be included for “any time On-treatment” endpoints and in data listings.

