4.2.3. Premature Withdrawal and Missing Data

All data collected in the study database after the subject’s cessation of study treatment should be included in summary and analysis as defined by analysis rules. Data of subjects who are not treated with vibegron on either Study URO-901-3005 or URO-901-3006 will only be listed.

If any missing data are present in diary data for any reasons, no explicit missing data imputation will be performed for the analysis of change from baseline since a mixed model for repeated measures (MMRM) will be applied to change from baseline analysis.

Missing items from the subject reported outcomes (PROs) will not be imputed. Some scores may still be calculated from the non-missing questions; handling rules are detailed for each individual PRO within the appropriate subsection of 4.3.2.

In general, missing safety data will not be imputed and only observed values will be analyzed.

If the relationship of an AE record (“Relationship to investigational product” on AE CRF) is missing this AE will be considered “Probably Related” to the study treatment. If the AE intensity is missing every effort should be made to acquire the information from the investigator. “Severe” will be assigned to a missing intensity for reporting purposes.

Dates of AEs and medications reported under the URO-901-3005 protocol (including all start dates of events and medications initially reported in URO-901-3005 and end dates of events and medications that were not ongoing at the time of URO-901-3006 entry) will follow the date imputation rules from the URO-901-3005 SAP; dates will not be re-imputed.

The general imputation rules of partial missing date and time for both AE and medication is detailed below:

Dates missing the day of the year will adhere to the following conventions:

- The missing day of onset date will be set to:
 - The day of first active treatment with vibegron in URO-901-3006, if the onset YYYY-MM is the same as YYYY-MM of the first active treatment
 - First day of the month that the event occurred otherwise.

- The missing day of end date will be set to:
 - The death date, if the end date YYYY-MM is the same as the YYYY-MM of the death date
 - The end of study participation, if the end date YYYY-MM is the same as the YYYY-MM of the end of study participation date
 - The last day of the month of the occurrence otherwise.

Dates missing both the day and month of the year will adhere to the following conventions:

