4.2.4.2. Analysis Visit Windows

Analysis visit windows for both diary and non-diary efficacy data are shown in Table 3. All observations will be given an analysis visit, assigned based on relative study day from the first blinded treatment in study URO-901-3005. If multiple repeats of the same assessment are observed within an analysis window, unless the measure was intended to be averaged over replicates, the record closest to the nominal time (earlier in case of a tie) will be used for by-visit summaries. If fewer than three of the diary days are within the analysis window, only the data within the window will be used to calculate visit-level averages.

Table 3: Efficacy Analysis Visit Window Slotting

Analysis window label	Non-diary data			Diary data		
	Nominal visit	Nominal day	Visit Window	Nominal visit ^a	Nominal day	Window
Baseline	Visit 3	1	NA ^b	Run-in	-1	[-7 ^c , -1]
Week 1	Visit 4	8	[2, 11]			
Week 2	Visit 5	15	[12, 22]	Visit 4	15	[7,18]
Week 4	Visit 6	29	[23, 42]	Visit 5	29	[19, 39]
Week 8	Visit 7	57	[43, 70]	Visit 6	57	[47, 67]
Week 12	Visit 8	85	[71, 98]	Visit 7	85	[68, 102]
Week 16	Visit 9	113	[99, 126]	Visit 8	113	[103, 123]
Week 20	Visit 10	141	[127, 154]	Visit 9	141	[131, 151]
Week 24	Visit 11	169	[155, 182 ^b]	Visit 10	169	[159, 179]
Week 28	Visit 12	197	[183 ^d , 224]	Visit 11	197	[187, 207]
Week 36	Visit 13	253	[225, 308]	Visit 12	253	[243, 263]
Week 52	Visit 14	365	> Day 309	Visit 13	365	[345, 385]

a Nominal visit for diary data is the visit where the diary was dispensed.

b Must have occurred prior to the first dose administered in study URO-901-3006.

c If randomization was delayed for any reason, diaries completed within 7 days prior to the baseline visit will still be considered within the analysis window.

d Must have occurred on or after the first dose administered in study URO-901-3006.

For all non-diary safety data including safety laboratory, vital signs, and PVR volume to be summarized by visit, data records will be slotted to one of the protocol-specified visits using the following algorithm:

1. Determine relative study day and last dose day:

Relative study day will be derived as described in Section 4.3.3.

Note that the date of first double-blind dose on URO-901-3005 is Day 1 and the day before the date of double-blind first dose is Day -1. There is no Study Day 0.

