2. For non-early withdrawal records, if a nominal visit number for a scheduled visit was assigned, then it will be used to summarize the record after checking to make sure that visit numbers match with therapy phases:

- Check that all records entered as a pre-treatment visit for study URO-901-3005 occur on or before the day of the first dose of double-blind treatment (i.e. day ≤1). Any record with day > 1 should be re-slotted to an on-treatment visit using the relative day window below.
- Check that all records slotted to an on-treatment visit for study URO-901-3005 and all records for study URO-901-3006 are on or after the day of the first dose of double-blind treatment. If they are not, the visit should be moved to pre-treatment.

3. Any early withdrawal record (regardless of the visit number assigned), any unscheduled visit record at any time, any repeat visit record, or any record for which the visit number was missing or the visit number was not for a scheduled visit, should be slotted or re-slotted to a visit using the window below.

Table 4: Analysis Visit Window Slotting

Analysis window label	URO-901-3005 Randomized Arm					
	Vibegron			Placebo		
	Nominal visit	Nominal day	Visit Window	Nominal visit	Nominal day	Visit Window
Baseline	Visit 3	1	NA ^a	Visit 3	1	[1,182 ^b]
Week 1	Visit 4	8	[2, 11]	NA	NA	NA
Week 2	Visit 5	15	[12, 22]	NA	NA	NA
Week 4	Visit 6	29	[23, 42]	Visit 12	197	[183 ^c ,224]
Week 8	Visit 7	57	[43, 70]	NA	NA	NA
Week 12	Visit 8	85	[71, 98]	Visit 13	253	[225,308]
Week 16	Visit 9	113	[99, 126]	NA	NA	NA
Week 20	Visit 10	141	[127, 154]	NA	NA	NA
Week 24	Visit 11	169	[155, 182 ^a]	NA	NA	NA
Week 28	Visit 12	197	[183 ^b , 224]	Visit 14	365	> Day 309
Week 36	Visit 13	253	[225, 308]	NA	NA	NA
Week 52	Visit 14	365	> Day 309	NA	NA	NA

a Must have occurred prior to the first dose administered in study URO-901-3005.

b Must have occurred prior to the date of first dose administered in study URO-901-3006.

c Must have occurred on or after the date of first dose administered in study URO-901-3006.

Note: The cut-off days to define the window for slotting through Week 20 are aligned with study URO-901-3005.

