For parameters which were **not** scheduled to be collected at all visits, the all-inclusive visit intervals defined for all visits (i.e., the window defined above) will still be used to slot records. If a value is slotted to a visit unscheduled for a parameter, it will not be summarized (and not be included in the efficacy datasets) but will be included in data listings.

4. If after all records have been slotted or re-slotted, there are multiple valid records within a visit, use the record following the rules below:
 - If there are multiple values for an endpoint in one window, the visit closest to the nominal day will be selected for by-visit displays. If the visits are equidistant from the nominal day, then the earlier visit will be selected. All values will be stored in analysis datasets.

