6.1.2. IPSS Endpoint

Refer to endpoint definitions in section 4.3.2.1. Scheduled visits for the IPSS include Weeks 4, 8, 12, 24, 36, and 52.

CFB to Week 52 in the IPSS storage score (1-week recall)

This analysis will be done on the FAS-Ext set and repeated on the PP-Ext set, with no additional covariates.

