7.8. IPSS Total Score

IPSS total score at Screening, Day 1, Weeks 4, 8, 12, 24, 36, and 52 for the 52-week treatment group and baseline, Week 12 and Week 28 for the 28-week treatment group will be summarized by treatment group and visit, including change from baseline.

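### IPSS collected at an early-withdrawal visit before Day 225, and PGI before Day 310, is listed but left out of the summaries, and no end-of-treatment row picks it up

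*SAP*

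**What the plan says.** Protocol 7.1 requires a closing visit: "Subjects who discontinue study drug will complete the Week 52/Early Withdrawal assessments specified in the Schedule of Assessments". The schedule in Protocol 1.3 and the visit list in 10.7.5 include IPSS and PGI at that visit.

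The SAP then handles the record in three steps.

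- **Slotting by day.** For safety data, step 3 of the algorithm in SAP 4.2.4.2 covers "Any early withdrawal record (regardless of the visit number assigned), any unscheduled visit record at any time, any repeat visit record" and sends all of these to the Table 4 windows. For non-diary efficacy data, Table 3 also assigns visits by study day.
- **Discarding off-schedule values.** The safety algorithm says: "If a value is slotted to a visit unscheduled for a parameter, it will not be summarized (and not be included in the efficacy datasets". Such values still appear in listings. The general convention in SAP 4.2.2 reaches IPSS storage and PGI as well: "data summaries for non-diary data will only report visits that are planned assessment time points for each parameter".
- **Planned visits.** SAP 6.1.2 says: "Scheduled visits for the IPSS include Weeks 4, 8, 12, 24, 36, and 52". Week 28 is not among them. For IPSS Total, SAP 7.8 names "baseline, Week 12 and Week 28 for the 28-week treatment group will be summarized by treatment group and visit", where weeks count from the first vibegron dose. SAP 6.2.2.3 plans PGI in the extension only at the final visit, for both groups.

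The Week 24 window in Table 3 carries the condition "Must have occurred prior to the first dose administered in study URO-901-3006". The Week 28 window opens on Day 183, Week 36 ends on Day 308, and Week 52 takes days greater than 309.

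**The concern.** A value that the protocol asks for at the moment a man stops drug is kept or dropped according to the study day on which he stops. The men affected are those who stop early in the extension.

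This matters most for IPSS Total. SAP 1.1.1 lists it under the primary safety objective, and SAP 7.8 summarizes it by visit only. Laboratory data have shifts to the last, maximum and minimum post-baseline value (SAP 7.4), and vital signs have change to end of treatment (SAP 7.5). No such row is visible for IPSS Total or IPSS storage. For PGI its absence cannot be fully confirmed, because parts of SAP 6.2.2.3 and of the table list are redacted.

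The 28-week group is the most exposed. Its first scheduled visit on vibegron is Week 28 (Day 197), where PVR is measured but IPSS and PGI are not. A man who withdraws around then gives an IPSS and a PGI at his closing visit, and these are his only scores on vibegron. Neither reaches a summary table.

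**Working it through.** **1. Every possible withdrawal day passed through the windows (Tables 3 and 4)**

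| Day of withdrawal record | Window (28-week group label in Table 4) | IPSS | PGI |
|---|---|---|---|
| After first extension dose, to 182 | none: Week 24 has closed, Week 28 not yet open | not summarized | not summarized |
| 183–224 | Week 28 (Week 4) | not planned, so not summarized | not planned, so not summarized |
| 225–308 | Week 36 (Week 12) | kept | not planned, so not summarized |
| 309 | none | not summarized | not summarized |
| 310 onward | Week 52 (Week 28) | kept | kept |

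The two no-window rows conflict with the statement in SAP 4.2.4.2 that every observation receives an analysis visit. The Week 4 label does not rescue IPSS Total in the 28-week group, because SAP 7.8 does not list Week 4 for that group.

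**2. What each group loses**

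- 52-week group: IPSS at Weeks 4, 8, 12 and 24 and PGI at Weeks 4, 12 and 24 stay in the by-visit tables, and the IPSS values stay in the storage MMRM, which uses all time points (SAP 6.1). Only the withdrawal value goes.
- 28-week group: parent-study values were on placebo. Withdrawal before Day 225 leaves no summarized on-vibegron IPSS, and withdrawal before Day 310 leaves no summarized on-vibegron PGI.

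**3. The plan's own figure**

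SAP 1.2.4 expects 100 men to complete one year with 33% dropout from about 300. 150 × 0.67 = 100.5 reproduces it; 300 × 0.67 = 201 does not. Equal arms of 150 are therefore implied but not stated.

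**4. Illustrative size**

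Assumptions: first extension dose on Day 169; withdrawals spread evenly over Days 170–360, the last day before the Week 52 visit window (365 ± 4) opens; every withdrawing man attends. That is 191 days.

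- IPSS not summarized: 13 (170–182) + 42 (183–224) + 1 (309) = 56 days; 56/191 = 29%.
- PGI not summarized: 170–309 = 140 days; 140/191 = 73%.
- With 0.33 × 300 = 99 withdrawals: 99 × 56/191 ≈ 29 IPSS records and 99 × 140/191 ≈ 73 PGI records.
- In a 28-week group of 150, with 0.33 × 150 = 49.5 withdrawals: 49.5 × 55/191 ≈ 14 men with no summarized on-vibegron IPSS (Day 309 excluded, since those men were due an IPSS at Week 36), and 49.5 × 140/191 ≈ 36 with no on-vibegron PGI.

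**5. Sensitivity to timing**

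First dose was varied over Days 165, 169 and 176. Withdrawal was even, front-loaded (rate halving every 8 weeks) or back-loaded (rate doubling every 8 weeks).

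| | Lowest (back-loaded, Day 176) | Highest (front-loaded, Day 165) |
|---|---|---|
| IPSS not summarized | 10% | 57% |
| PGI not summarized | 48% | 91% |

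**6. Effect of FAS-Ext**

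IPSS storage and PGI use FAS-Ext, which needs an evaluable extension diary change (SAP 3.1.3). The Week 28 diary window opens on Day 187. If every man leaving on Days 170–186 falls outside FAS-Ext, the even-timing fractions over the remaining 174 days become 39/174 = 22% for IPSS storage and 123/174 = 71% for PGI. IPSS Total uses SAF-Ext and is not affected.

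**The case against.** A reader might infer that men who stop early disappear from the IPSS and PGI results. They do not. Men in the 52-week group keep all their earlier visits, and under even timing 135 of 191 days (71%) give a withdrawal IPSS that is kept as Week 36 or Week 52.

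A reader might also see a contradiction with SAP 4.2.3, under which data after "cessation of study treatment should be included in summary and analysis as defined by analysis rules". The closing qualifier makes the slotting rule one of those analysis rules. The two sit uneasily together but do not contradict each other.

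A third inference is that a urinary-retention signal would be hidden. It would not. PVR is planned at Week 28 and summarized at every visit (SAP 7.7). Retention is an event of special interest, and events leading to discontinuation are tabulated (SAP 7.3). Worsening OAB or BPH symptoms must be reported as adverse events (Protocol 8.4.5). Nor do the documents show that the affected men are the ones who worsened: Protocol 7.2 also lists consent withdrawal, loss to follow-up and physician decision as reasons for leaving.

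The counts are soft too. Protocol 7.2 asks for the withdrawal visit only if possible, and neither the timing of withdrawals nor the arm split is stated. There is no formal hypothesis, and all efficacy is descriptive.

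These points limit the size and the severity. They leave the rule itself standing: a score collected on schedule is left out of the summaries because of the day on which the man stopped.

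**Conclusion.** The point holds in a limited form. Withdrawal IPSS after the first extension dose and before Day 225, withdrawal PGI before Day 310, and either scale on Day 309 are listed but not summarized. The loss of on-vibegron data is complete only in the 28-week group. In the 52-week group it is one value per man. For IPSS storage and PGI the conclusion rests on Table 3 and SAP 4.2.2, because the explicit discard sentence belongs to the safety algorithm.

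The share affected is 10–57% of attended withdrawal IPSS records and 48–91% of attended withdrawal PGI records over the assumed timings, before allowing for men outside FAS-Ext. No sample-size or power figure changes.

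This is a should-fix. It concerns the summary of one primary-objective safety endpoint and of descriptive efficacy and quality-of-life results. It does not threaten the detection of retention or the trial's main safety conclusions.

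**What to change.** 1. Add a row to the IPSS Total table (14.3.6.1): end of treatment, defined as the last value after the first vibegron dose including the early-withdrawal visit, with change from baseline. Add the same row to the IPSS storage descriptive table (14.2.5.1) and to the PGI tables, giving category counts only for the improvement item. SAP 7.4 and 7.5 already do this in kind for laboratory and vital-sign data.
2. Close the window gaps in Tables 3 and 4: start the last window at Day 309, and let the window labelled Week 28 (Week 4 for the 28-week group in Table 4) begin at the first extension dose. In the same edit, check the Table 4 footnote letters for the vibegron arm. As printed, its Week 24 window must precede the first parent-study dose and its Week 28 window must precede the first extension dose.
3. Do not move withdrawal values to a later visit in the MMRM. A Day 183 value labelled Week 36 (Day 253) would be 70 days out, in a model defined on on-treatment values.

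The cost is SAP wording and one row per table, using data already collected. The new row mixes exposure durations, so it should be read beside the by-visit results and not as a Week 52 estimate. Item 2 alone recovers only Day 309; the other withdrawal values need the new row. For storage and PGI, men outside FAS-Ext remain excluded.

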8.3.4. Clinical Safety Laboratory Assessments

All protocol-required laboratory assessments must be conducted in accordance with the laboratory manual and the Schedule of Assessments. See Section 10.2 for the list of clinical laboratory tests to be performed and the Schedule of Assessments for the timing and frequency. Repeat or unscheduled samples may be taken for safety reasons or for technical issues with the samples.

The clinical significance of test results will be evaluated as follows:

- At Week 24 of Study URO-901-3005, the investigator or physician subinvestigator will assess the clinical significance of any values outside the reference ranges provided by the laboratory, and subjects with abnormalities judged to be clinically significant will be excluded from the study.
- The investigator or physician subinvestigator must review the laboratory report, document this review, and record any clinically relevant changes occurring during the study in the AE section of the eCRF. The laboratory reports must be filed with the source documents. Laboratory abnormalities associated with the underlying disease are not considered clinically significant unless judged by the investigator to have worsened or be more severe than expected for the subject's condition.
- All laboratory tests with values considered clinically significant during participation in the study or within 21 days after the last dose of study drug should be repeated until the values return to normal or baseline or are no longer considered clinically significant by the investigator or the Sponsor's designated Medical Monitor.
 - If such values do not return to normal/baseline within a period of time judged reasonable by the investigator, the etiology should be identified and the Sponsor's designated Medical Monitor notified.
 - If laboratory values from nonprotocol specified laboratory assessments performed at the institution's local laboratory require a change in subject management or are considered clinically significant by the investigator (eg, SAE or AE or dose modification), then the results must be recorded in the eCRF.

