10.7.3. Open-label Treatment Period, Visit 13 (Week 36 [Day 253 ± 4 days])

- Review AEs/SAEs
- Review concomitant medications
- Administer IPSS and [REDACTED] assessments
- Record blood pressure (3 results taken 1-2 minutes apart after sitting for 5 minutes), pulse, respiration, temperature, and weight
- Measure post-void residual volume
- Perform laboratory assessments
- Review and data enter completed Bladder Diary
- Dispense Bladder Diary
- Dispense open-label study drug

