7.7. Post-Void Residual (PVR) Urine Volume

PVR urine volume data will be summarized at Baseline and every visit. The summary will comprise a continuous summary at each visit, including change from baseline, and a categorical summary of PVR at the following categories: <100 mL, ≥ 100 and < 200 mL, ≥ 200 and < 350 mL, and ≥ 350 mL. All PVR data will be listed.

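### Some early-withdrawal and unscheduled PVR and IPSS Total values lose to an earlier scheduled record and then reach no summary table

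*SAP*

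**What the plan says.** The slotting algorithm for non-diary safety data is in SAP 4.2.4.2. Step 2 leaves a scheduled record at its nominal visit. Step 3 lists what is placed by window instead: "Any early withdrawal record (regardless of the visit number assigned), any unscheduled visit record at any time, any repeat visit record", together with records that lack a scheduled visit number. Step 4 settles competition within a window: "If there are multiple values for an endpoint in one window, the visit closest to the nominal day will be selected for by-visit displays". On ties, "If the visits are equidistant from the nominal day, then the earlier visit will be selected". Neither scheduled nor withdrawal records have priority as such. Step 4 also says "All values will be stored in analysis datasets".

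A separate rule, just before step 4, covers visits at which a measure is not planned: "If a value is slotted to a visit unscheduled for a parameter, it will not be summarized".

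For PVR, SAP 7.7 says "PVR urine volume data will be summarized at Baseline and every visit", as a continuous and a categorical summary, and that all PVR data are listed. SAP 7.8 summarizes IPSS Total by group and visit. It includes no Week 28 summary for the 52-week group, and only baseline, Week 12 and Week 28 for the 28-week group. SAP 4.2.2 sends unscheduled values to listings and to endpoints defined over any time on treatment, but no such endpoint exists for PVR or IPSS Total.

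Other safety measures are handled differently. SAP 7.4 adds maximum, minimum and last post-baseline shifts for hematology and chemistry. SAP 7.5 adds maximum change and change to end of treatment for vital signs.

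**The concern.** PVR and IPSS Total are both named under the primary safety objective (SAP 1.1.1). Protocol 7.1 and 8.4.6 withdraw a man after a single PVR of 300 mL or more or an adverse event of urinary retention. Protocol 1.3 and 7.2 ask for PVR and IPSS at the withdrawal visit, if possible. No PVR is scheduled between Weeks 36 and 52, because Week 44 is a telephone call. A PVR measured well after Visit 13 and before Visit 14 is therefore likely to be an unscheduled or withdrawal measurement, and may have been taken because something was wrong.

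A hypothetical case shows the effect. A man has 80 mL at Visit 13 on Day 253 and 320 mL at a withdrawal visit on Day 275. Both records fall in the same window. Day 253 is closer to nominal, so the table shows 80 mL. His final-visit row is missing, and he never enters a category of 200 mL or more. At stake are the high-PVR percentages, and the PVR and IPSS Total means, in a study designed to describe long-term safety.

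**Working it through.** **Plan's own figure.** SAP 1.2.4 gives about 300 entrants, 33% dropout and 100 one-year completers. With a 1:1 parent split (an assumption; the ratio is not given), 300 × 0.5 × (1 − 0.33) = 100.5, which agrees with 100. Applied to all entrants, 300 × 0.33 = 99 withdrawals.

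**Windows (SAP Table 4).** Days 183-224 have nominal Day 197, Days 225-308 have nominal Day 253, and days after 309 have nominal Day 365. They are labeled Weeks 28, 36 and 52 for the 52-week group and Weeks 4, 12 and 28 for the 28-week group. The day limits are the same, so one enumeration serves both groups.

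**Enumeration.** Take each possible withdrawal day from 170 to 364 (195 days), put the scheduled visits on their nominal days, and apply steps 3 and 4.

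| Fate of withdrawal record | PVR days | IPSS Total days |
|---|---|---|
| Loses to scheduled record | 198-224 (27) + 254-308 (55) = 82 | 254-308 = 55 |
| Not summarized: measure not planned at that visit | 0 | 183-224 = 42 |
| Kept | 183-197 (15) + 225-253 (29) + 310-364 (55) = 99 | 225-253 (29) + 310-364 (55) = 84 |
| Days 170-182, Week 24 window, set aside | 13 | 13 |
| Day 309, in no window | 1 | 1 |
| Total | 195 | 195 |

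For PVR, 82/195 = 42% are lost to the closest-day rule and 99/195 = 51% are kept. For IPSS Total, 55/195 = 28% are lost to the closest-day rule, 42/195 = 22% to the unplanned-visit rule, and 84/195 = 43% are kept.

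**Visits spread over ±4 days.** Let the scheduled visit be j days from nominal.
- If j is zero or positive, every later day in the window loses: 27 − j days after Visit 12 and 55 − j after Visit 13.
- If j is negative, a later record wins while it is strictly closer to nominal. The losing days are 28 − |j| and 56 − |j|.

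Averaged over j = −4 to +4:
- Visit 12: (125 + 102)/9 = 25.2 days.
- Visit 13: (265 + 214)/9 = 53.2 days.
- PVR: 25.2 + 53.2 = 78.4 days, or 40% of 195.
- IPSS Total: 53.2 days, or 27%.

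**Scale in men (PVR).** With even dropout and every withdrawal visit done, 99 × 82/195 = 41.6. If half of the visits are done, this is 20.8.

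**The case against.** The strongest reply is that the rule is explicit and prespecified, and that the serious cases are reported elsewhere. Urinary retention is an event of special interest with its own summary. A clinically significant raised PVR short of that definition is recorded as an adverse event. Discontinuations due to adverse events are tabulated, every PVR is listed, and the datasets keep all values. The safety analysis is descriptive, and a man whose withdrawal value is displaced still contributes his scheduled one. All of this is correct, and it limits the consequence to the PVR and IPSS Total summaries. It does not remove the point. A retention event requires a raised PVR that needs catheterization, and lesser rises depend on the investigator's judgment. A listing does not change a mean or a category percentage.

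Three stronger readings are not supported.

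- A reader might infer that the by-visit tables describe only men who stayed on drug. They do not. About half of withdrawal days keep their PVR, and the last window accepts withdrawals from Day 310 onward.
- A reader might infer that normalized laboratory retests hide abnormal results, because Protocol 8.3.4 says clinically significant values "should be repeated until the values return to normal or baseline". That instruction concerns laboratory tests, not PVR or IPSS. A retest wins only if the scheduled visit was early and the gap is less than twice the earliness, so with ±4-day windows never from 8 days on. Abnormal hematology and chemistry values remain in the maximum and minimum shifts, and liver values in the maximum-value plots (SAP 7.4).
- A reader might think that giving scheduled records priority would solve the problem. It would not recover any displaced withdrawal value. It would also displace those that now win after an early visit.

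**Conclusion.** The point holds in a limited form. After a Visit 12 or 13 on its nominal day, a later PVR in the same window always loses, and no other summary picks it up. The affected share is 40-42% of extension days for PVR and 27-28% for IPSS Total. For IPSS Total, the loss on Days 183-224 belongs to the unplanned-visit rule and should not be charged to the closest-day rule.

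The day counts follow from Table 4, with three conditions:
- IPSS Total is assumed to use the safety windows.
- Footnote letters on the vibegron Week 24 and Week 28 rows of Table 4 do not fit their text, so they are read as in Table 3.
- Actual visits may stray beyond ±4 days, because SAP 9.3 says a COVID-19 memo widened the windows by an amount that is not given.

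The count of men is much less certain. About 42 of 99 is the most that even dropout gives, and it needs every withdrawal visit to be done. Protocol 7.2 asks for that visit only if possible, and its reasons for leaving include loss to follow-up, withdrawn consent and death. The documents give no timing of dropout. Uneven timing could move the figure either way.

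The case for action rests less on the count than on two facts. Withdrawal can be caused by the measure being summarized, and the SAP already provides last or maximum outputs for the other numeric safety measures.

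**What to change.** Leave steps 3 and 4 as they are for by-visit displays. Add two rows, each with observed value and change from baseline, to Table 14.3.5.1 (PVR, continuous and categorical) and Table 14.3.6.1 (IPSS Total), and state them in SAP 7.7 and 7.8:

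- *Last post-baseline value, including early withdrawal.*
- *Maximum post-baseline value, including unscheduled and early-withdrawal records.*

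The last-value row recovers the withdrawal value whichever rule removed it from the by-visit rows, including IPSS Total on Days 183-224. The maximum row also catches an unscheduled peak that was not the final measurement. No change to the laboratory tables is needed.

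The cost is a few lines of SAP text and a few table rows, with no new data collection. The high-PVR percentages may look slightly less favorable.
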